### **MODIFICATION HISTORY**

Unique	Date of the		
Identifier for	Document		Significant Changes from
this Version	Version	Author	Previous Authorized Version
V1.0	25APR2019	[name]	Not applicable, first version

 ${\tt Document:} \qquad {\tt \underline{\label{losdata}Palladio}\label{losdata} Palladio} \\ {\tt \underline{\label{losdata}}\label{losdata} Palladio} \\ {\tt \underline{\label{losdata}}\label{losdata} Palladio} \\ {\tt \underline{\label{losdata}}\label{losdata} Palladio} \\ {\tt \underline{\label{losdata}}\label{losdata}\label{losdata} Palladio} \\ {\tt \underline{\label{losdata}}\label{losdata}\label{losdata}\label{losdata} Palladio} \\ {\tt \underline{\label{losdata}}\label{losdata}\label{losdata}\label{losdata}\label{losdata}\label{losdata}\label{losdata} Palladio \\ {\tt \underline{\label{losdata}}\label{losdata}\label{losdata}\label{losdata}\label{losdata}\label{losdata}\label{losdata}\label{losdata}\label{losdata}\label{losdata}\label{losdata}\label{losdata}\label{losdata} Palladio \\ {\tt \underline{\label{losdata}}\label{losdata}\l$ 

102 SAP V1.0 NonPKPD 25APR2019

Author: [name] Version Number: 1.0

Version Date: 25 April 2019

Template No: CS\_TP\_BS016 – Revision 5 Reference: CS\_WI\_BS005

Effective Date: 01Apr2018

Palladio Biosciences STATISTICAL ANALYSIS PLAN: PROTOCOL PA-102 Page 4 of 36

1.0 Version Date: 25 April 2019

Template No: CS\_TP\_BS016 – Revision 5 Reference: CS\_WI\_BS005

Effective Date: 01Apr2018

Palladio Biosciences STATISTICAL ANALYSIS PLAN: PROTOCOL PA-102 Page 8 of 36

### 1. Introduction

This document describes the rules and conventions to be used in the presentation and analysis of efficacy and safety data for Protocol PA-102. It describes the data to be summarized and analyzed, including specifics of the statistical analyses to be performed.

This statistical analysis plan (SAP) is based on protocol version 5, dated 21 March 2019.

A separate pharmacokinetics/pharmacodynamics (PK/PD) SAP will be written by IQVIA PK and will describe the analysis and presentation of PK and PD data for Protocol PA-102.

### 2. STUDY OBJECTIVES

### 2.1. PRIMARY OBJECTIVE

The primary objectives of this study are:

- To characterize the safety and tolerability of lixivaptan following multiple doses in autosomal dominant polycystic kidney disease (ADPKD) subjects with relatively preserved kidney function (chronic kidney disease stage 1 [CKD1] and stage 2 [CKD2]) and moderately impaired renal function [CKD3].
- To characterize the PK profile of lixivaptan and its major metabolites (WAY-141624, WAY-138451, and WAY-138758) following multiple doses of lixivaptan in ADPKD subjects with relatively preserved kidney function (CKD1 and CKD2) and moderately impaired renal function (CKD3).

 ${\tt Document:} \qquad {\tt \underline{\label{losdata}Palladio}\Lixivaptan} \\ {\tt WYA34000} \\ {\tt Biostatistics}\\ {\tt Documentation}\\ {\tt SAP}\\ {\tt PA-boundary}\\ {\tt PA-boundary}\\ {\tt SAP}\\ {\tt SAP}\\$ 

102 SAP V1.0 NonPKPD 25APR2019 Author: [name]

Version National 1.0

Version Date: 25 April 2019

Version Number:

Template No: CS TP BS016 – Revision 5 Reference: CS WI BS005

Effective Date: 01Apr2018

Palladio Biosciences STATISTICAL ANALYSIS PLAN: PROTOCOL PA-102 Page 9 of 36

## 2.2. SECONDARY OBJECTIVES

The secondary objectives of this study are:

- To characterize the effect of lixivaptan on urine osmolality over a 24-hour period following multiple doses of lixivaptan in ADPKD subjects; and
- To characterize the time course of the pharmacodynamic effect of lixivaptan on urine output, total kidney volume, liver volume, plasma copeptin and serum creatinine in ADPKD subjects.

### 3. STUDY DESIGN

## 3.1. GENERAL DESCRIPTION

This is a Phase 2, open-label, parallel-group, multiple dose study designed to evaluate the PK, pharmacodynamic (PD), safety and tolerability of multiple twice daily (BID) doses of 50 mg and 200 mg lixivaptan in ADPKD subjects with chronic kidney disease in stages CKD1, CKD2 or CKD3. Enrolled subjects will be assigned according to CKD classification to take one of 2 lixivaptan oral dose regimens for 7 days as shown below (Table 1). Each dose regimen includes morning (AM) and evening (PM) oral administration of lixivaptan.

Table 1 Chronic Kidney disease Classification Summary by Cohort and Dose Group

CKD Stage	Cohort	N	eGFR a	Dose
CKD1 or CKD2	1	8	eGFR $\geq$ 60 mL/min/1.73 m 	200 mg BID
CKD3	2	8	eGFR $\geq$ 30 to < 60 mL/min/1.73 m 	200 mg BID
CKD1 or CKD2	3	8	eGFR $\geq$ 60 mL/min/1.73 m 	50 mg BID
CKD3	4	8	eGFR $\geq$ 30 to < 60 mL/min/1.73 m 	50 mg BID

Abbreviations: CKD=chronic kidney disease; eGFR=estimated glomerular filtration rate; BID=twice daily.a eGFR is calculated by the 2009 Chronic Kidney Disease Epidemiology Collaboration (CKD-EPI) equation.

Document: \(\liedc-vnasc01\BIOSdata\Palladio\Lixivaptan\WYA34000\Biostatistics\Documentation\SAP\PA-102 SAP V1.0 NonPKPD 25APR2019

Author: [name] Version Number:

Version Date: 1.0
Version Date: 25 April 2019

Template No: CS\_TP\_BS016 – Revision 5 Reference: CS\_WI\_BS005

Effective Date: 01Apr2018

Palladio Biosciences STATISTICAL ANALYSIS PLAN: PROTOCOL PA-102 Page 10 of 36

Approximately 32 subjects (or more as necessary to achieve 32 study completers) will be enrolled at approximately 15 sites in the United States (US). Subjects will take one of 2 lixivaptan oral dose regimens for 7 days and will be allocated to one of 4 cohorts depending on CKD status. At least 2 males or females will be included in the 8 subjects assigned to each cohort (i.e. can be up to a 25%/75% split of male/female or 75%/25% split of male/female). The 200 mg BID dose cohorts will be enrolled first.

The study includes a screening period of up to 42 days. Subjects will be confined to the clinical research unit (CRU) on 2 separate occasions, with a total period of confinement of up to 7 days and 5 nights. The first confinement period will last up to 4 days (up to 3 nights), and the second confinement period will last 3 days (2 nights). Subjects will return to the CRU on an outpatient basis on Day 4 and Day 6 in the morning for a trough PK assessment. Except for the AM and PM doses on Days 1, 6 and 7, and the AM doses on Days 2, 4 and 6, all other doses will be self-administered by the subject. Subjects will return on Day 35 (±2) for end of study (EOS) assessments.

### 3.2. SCHEDULE OF EVENTS

Schedule of events can be found in Section 12.2 of the protocol.

### 3.3. CHANGES TO ANALYSIS FROM PROTOCOL

There are no meaningful changes in the analysis plans relative to the study protocol.

Document: \\ieedc-vnasc01\BIOSdata\Palladio\Lixivaptan\WYA34000\Biostatistics\Documentation\SAP\PA-

Author: [name] 25APR2019

[name] Version Number:

Version Date: 25 April 2019

Template No: CS\_TP\_BS016 – Revision 5 Reference: CS\_WI\_BS005

Effective Date: 01Apr2018

Palladio Biosciences STATISTICAL ANALYSIS PLAN: PROTOCOL PA-102 Page 11 of 36

### 4. PLANNED ANALYSES

## 4.1. DATA MONITORING COMMITTEE (DMC)

There is no DMC for this study requiring statistical outputs.

## 4.2. INTERIM ANALYSIS

No interim analysis is planned for this study.

### 4.3. FINAL ANALYSIS

All final, planned analyses of safety and efficacy data identified in this SAP will be performed by IQVIA Biostatistics, following Palladio authorization of this SAP, identification of major protocol deviations requiring analysis exclusions, database lock, and determination of analysis sets.

#### 5. ANALYSIS SETS

### **5.1.** ALL SUBJECTS ENROLLED SET

The all subjects enrolled set will contain all subjects who provide informed consent for this study. Subjects in this population will be used for disposition summaries, and where appropriate, will be analyzed according to cohort allocation. Subjects not allocated to a cohort due to screen failure will be indicated as Not Allocated.

Document: \\ieedc-vnasc01\BIOSdata\Palladio\Lixivaptan\WYA34000\Biostatistics\Documentation\SAP\PA-

4 102 SAP V1.0 NonPKPD 25APR2019
Author: [name]

Version Number: 1.0

Version Date: 25 April 2019

Template No: CS\_TP\_BS016 – Revision 5 Reference: CS\_WI\_BS005

Effective Date: 01Apr2018

Palladio Biosciences STATISTICAL ANALYSIS PLAN: PROTOCOL PA-102 Page 12 of 36

### 5.2. SAFETY ANALYSIS SET

The safety analysis set will contain all subjects who receive at least one dose of study medication and will be analyzed according to treatment received. This analysis set will be used for the safety analyses and for summarization of baseline/demographic characteristics.

### 6. GENERAL CONSIDERATIONS

Some minor modifications may be necessary to the planned design of tables, figures, and listings to accommodate data collected during the actual study conduct.

### **6.1. SUMMARY STATISTICS**

For categorical variables, the analysis set size (N for sample size and n for available data) and percentage (of available data) for each class of the variable will be presented. Percentages will be based on the number of subjects within the relevant analysis set and/or the number of subjects with data available.

All continuous variables will be summarized using descriptive statistics, including number of non-missing observations (n), mean, standard deviation (SD), median, minimum and maximum values.

### 6.2. REFERENCE START DATE AND STUDY DAY

Study day will be calculated from the reference start date and will be used to show the start/stop day of assessments and events.

Document: \\ieedc-vnasc01\BIOSdata\Palladio\Lixivaptan\WYA34000\Biostatistics\Documentation\SAP\PA-

4 102 SAP V1.0 NonPKPD 25APR2019
Author: [name]

Version Number: 1.0

Version Date: 25 April 2019

Template No: CS\_TP\_BS016 – Revision 5 Reference: CS\_WI\_BS005

Effective Date: 01Apr2018

Palladio Biosciences STATISTICAL ANALYSIS PLAN: PROTOCOL PA-102

Page 13 of 36

The reference start date is defined as the day of the first dose of study medication (Day 1 is the day of the first dose of study medication). Study day will be calculated relative to reference start date and will appear in every listing where an assessment date or event date appears.

If the date of the event is on or after the reference date, then:

Study Day = (date of event - reference date) + 1.

If the date of the event is prior to the reference date, then:

Study Day = (date of event – reference date).

If the event date is partial or missing, the study day and any corresponding durations will be missing in the listings.

#### 6.3. **BASELINE**

Unless otherwise specified, baseline is defined as the last non-missing measurement taken prior to reference start date (including unscheduled assessments). In the case where the last non-missing measurement and the reference start date coincide, that measurement will be considered pre-baseline, but Adverse Events (AEs) and medications commencing on the reference start date will be considered post-baseline.

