5.3 Treatments Administered

Subjects assigned to one of the 2 dose levels of lixivaptan (Table 5-1) will receive oral lixivaptan BID (AM and PM) from Day 1 through Day 7. The PM dose will be administered approximately 10 hours after the AM dose.

Table 5-1 Study Cohorts and Lixivaptan Dose Levels

Cohort	CKD stage	Dose*	N	
1	CKD1 or CKD2	200 mg BID	8 subjects	Candidate maximum tolerated dose
2	CKD3	200 mg BID	8 subjects	
3	CKD1 or CKD2	50 mg BID	8 subjects	Candidate lowest effective dose
4	CKD3	50 mg BID	8 subjects	

*PM dose to be administered approximately 10 hours after the AM dose

Prior to the morning doses on Days 1 and 7, subjects will fast overnight for ≥ 8 hours prior to study medication administration. Water will be allowed *ad libitum* during the overnight fasting. Liquids (other than water) are considered part of the ≥ 8 hour overnight fast.

In the morning of Days 1 and 7, subjects will receive lixivaptan with room temperature water (approximately 240 mL [8 ounces]) and will remain fasted for 2 hours after dosing. Water

will be allowed *ad libitum* during the 2 hours fasting, however subjects will be required to abstain from consuming other liquids until 2 hours after dosing.

The evening doses on Days 1 and 7 will be administered in the CRU under fasting conditions, i.e. 2 hours before and 2 hours after meals. Liquids (other than water) are considered part of the 2 hour fast.

Study drug will be administered orally to subjects. Administration of each dose of study drug while the subject is confined at the CRU will be supervised, verified, and documented according to the CRU's standard operating procedures. A mouth and hand check will be performed immediately after study drug administration.

The actual date and time of each dose administration will be entered in the eCRF.

When not confined to the CRU, subjects will self-administer lixivaptan with water (approximately 240 mL) and without fasting. Subjects will continue to adhere to the recommended fluid intake regimen outlined in [Section 5.9](#).

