7.7.3 Safety Analyses

Clinical Laboratory Tests

All laboratory data will be summarized by renal function group and at each scheduled timepoint using descriptive statistics (n, mean, SD, median, minimum, and maximum).

The baseline value is the last value observed prior to first administration of study drug and any information taken after first administration of study drug is regarded as post baseline information. The change-from-baseline variables will be calculated as the post-baseline value minus the value at baseline. Change from baseline on continuous data will be summarized using descriptive statistics at each scheduled time point by renal function group. For categorical data, change-from-baseline will be summarized using frequency and proportion at each scheduled timepoint by renal function group.

Individual data listings of laboratory results will be presented for each subject. Values outside of the laboratory's reference range (i.e., those with low or high values) will be flagged in the laboratory listings.

For all continuous laboratory variables, a shift table comparing the baseline value (normal, low, and high) to last observation on treatment will be presented.

For urinalysis, a shift table comparing the baseline value to the maximum value will be presented by renal function group (using number of subjects with results of negative, trace, or positive).

ECGs

A listing will be provided for Investigator-identified ECG abnormalities from safety ECGs. Overall evaluation of safety ECGs will be summarized by renal function group using frequency counts and percentage of subjects as normal or abnormal, and the relevance of the abnormality will be summarized by CS or NCS.

In addition, a summary shift table comparing baseline interpretation (normal, abnormal - NCS, abnormal - CS) to the Investigator interpretation at each time point will also be presented.

Continuous ECG parameters including heart rate, ventricular rate, PR interval, QRS duration, QT interval (uncorrected), and QTcF interval will be summarized for renal function group and over each scheduled timepoint in terms of absolute values using descriptive statistics (n, mean, SD, median, minimum, and maximum).

Vital Signs

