Changes from baseline in vital signs at each scheduled timepoint will be summarized by renal function group for the Safety Analysis Set using descriptive statistics (n, mean, SD, median, minimum, and maximum). The baseline value is defined as the last value observed prior to first administration of study drug. The change from baseline is defined as the post-baseline value minus the baseline value. There will not be any imputation for missing values. All vital sign data will be listed individually by each subject based on the Safety Analysis Set.

Physical Examinations

Changes in baseline in physical examination findings (Normal, Abnormal-NCS, Abnormal-CS) will be summarized using counts and percentages for renal function group and will also be listed individually for each scheduled timepoint.

Adverse Events

An overall summary of the number and percentage of subjects in each category will be presented, as will an overall summary of the number of events in each category. The number and percentage of subjects reporting AEs in each category above will be summarized by renal function group according to the system organ class (SOC) and preferred term (PT) assigned to the event using MedDRA.

All AE data will be listed for all subjects. Both the Investigator's verbatim terms and the MedDRA preferred terms will be listed for each subject. Listings will also include the SAEs, start and end time and date of AEs, relationship to study drug, severity, and action taken for the AEs. A summary of deaths (for all deaths, AE outcome, not AE term, is death) will be provided by number and percentage of subjects by renal function group.

Questionnaire for Tolerability

Tolerability data obtained from the questionnaire will be listed and summarized as detailed in the SAP.

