- ⁵ Clinical labs: hematology, clinical chemistry (including liver function), and urinalysis at approximately the same time of day (in the morning and, on dosing days, before the lixivaptan dose). The list of analytes is shown in [Table 6-1](#). Lab tests that need to be repeated during Screening may be obtained through the services of an at-home nursing service provided by the Sponsor.
- ⁶ Serum creatinine will be measured as part of the clinical laboratory assessment.
- ⁷ 12-lead ECG at Screening, Day 1 pre-dose, and prior to discharge from clinic on Day 8. Electrocardiograms to be obtained following 5 minutes rest in supine or semi-recumbent position. The same position must be used throughout the study for a given subject.
- ⁸ Vital signs will be measured following 5 minutes rest in a seated position. Systolic and diastolic blood pressure, pulse rate, respiratory rate, body temperature will be measured at the following time points: prior to Day -1 procedures, prior to discharge from CRU on Day 8, and at the End of Study visit. In addition, blood pressure and pulse rate will also be measured before each administration of study medication in the CRU.
- ⁹ Complete physical examination at Screening, and prior to discharge on Day 8. Brief physical examination on Day -2 or Day -1. Symptom-directed physical examinations as needed.
- ¹⁰ Adverse events and SAEs that are related to study participation (e.g., protocol-mandated intervention) will be recorded from the time the subject signs the informed consent form until exit from the study. All other AEs and SAEs will be recorded from the first dose of lixivaptan until exit from the study.
- ¹¹ Record daily fluid intake on Day -1, Day 1 and Day 7. On Day -1, measurement will begin 24 hours before the expected time of first study medication on Day 1 AM. On Day 1 and Day 7, measurements will begin immediately before the AM dose and will continue for 24 hours into the morning of Day 2 and Day 8, respectively.
- ¹² Subjects will take study medication in the AM and PM for 7 days. Subjects will be asked to record each dose of the study product taken on an outpatient basis in the Study Dosing Diary. Subjects will be asked to bring the Study Dosing Diary together with their unused study product at each visit to the CRU.
- ¹³ PK blood collection timepoints:
Day 1: 0, 1, 2, 4, 6, 9, 10, 11, 12, 14, and 16 hours post AM dose. The collections at 0 and 10 hours are immediately before the AM and PM doses, respectively;

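### Non-PK/PD SAP 6.3 sets baseline by calendar date, so the literal blood pressure and pulse baseline is the Day 1 reading taken after the first dose

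*SAP*

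**What the plan says.** The Non-PK/PD SAP builds its baseline in two steps. Section 6.2 fixes the anchor: "The reference start date is defined as the day of the first dose of study medication". Section 6.3 then says that, unless otherwise specified, "baseline is defined as the last non-missing measurement taken prior to reference start date (including unscheduled assessments"). For a last measurement that falls on the anchor date, 6.3 adds: "that measurement will be considered pre-baseline, but Adverse Events (AEs) and medications commencing on the reference start date will be considered post-baseline". Neither section mentions the time of dosing. Section 16.5, which specifies the vital-sign tables, asks for change and shift from baseline but gives no baseline definition of its own. Section 3.3 states: "There are no meaningful changes in the analysis plans relative to the study protocol".

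Protocol 7.7.3 uses the dose, not the date. For vital signs: "The baseline value is defined as the last value observed prior to first administration of study drug". For laboratory data it takes the same anchor and adds that "any information taken after first administration of study drug is regarded as post baseline information".

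On timing, footnote 8 to protocol Table 12-1 says "blood pressure and pulse rate will also be measured before each administration of study medication in the CRU". Both Day 1 doses are given in the unit. Protocol 3.1 excludes them from self-administration, and 5.3 says of the second: "The evening doses on Days 1 and 7 will be administered in the CRU under fasting conditions".

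**The concern.** Every subject has two scheduled Day 1 blood pressure and pulse readings with the same date, one before any drug and one after the first dose. A rule that sees only the date cannot separate them. If Day 1 values are eligible, the word last picks the later one.

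Vital signs are part of the safety and tolerability primary endpoint (protocol 2.2.1), and protocol 1.6 lists orthostatic hypotension and tachycardia among the most common adverse events in earlier lixivaptan studies. With an on-drug baseline, any first-dose effect on seated pressure or pulse that persists to the evening would be subtracted from every later change. The only scheduled on-drug change within Day 1 would disappear, because that reading would itself be the baseline. The baseline would also be an evening reading, set against morning readings on other days.

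**Working it through.** The plan states no figure to reproduce here. The check applies each rule to the schedule.

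**Time of the second Day 1 reading.** Protocol 3.1 places the in-unit PM dose 10 ± 0.25 h after the AM dose. Protocol Table 12-2 allows predose vital signs up to 60 minutes before a dose.

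- Earliest: 10 − 0.25 − 1 = 8.75 h after the first dose.
- Latest: 10 + 0.25 = 10.25 h after the first dose.

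**Blood pressure and pulse baseline under each rule**

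| Rule | Value selected |
|---|---|
| Protocol 7.7.3: before first administration | Day 1, before the AM dose |
| SAP 6.3, Day 1 values eligible | Day 1, before the PM dose |
| SAP 6.3, Day 1 values not eligible | Day -1 |

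Neither date-only reading selects the protocol's value. Reaching it requires a time condition that 6.2 and 6.3 do not contain.

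**Effect on a later change.** Let Y be a later reading, and AM and PM the two Day 1 readings. Then

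(Y − PM) − (Y − AM) = −(PM − AM).

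Each later change in a subject moves by minus that subject's Day 1 difference. With complete data, a cohort's mean change moves by minus the cohort's mean Day 1 difference. In the shift table, the baseline category changes for any subject whose value crosses a limit in SAP Table 3 between the two readings, for example 140 mmHg systolic or 100 bpm.

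**How many readings are touched.** After the first dose, the scheduled points are Day 1 pre-PM; pre-AM on Days 2, 4, 6 and 7; pre-PM on Days 6 and 7; Day 8; and End of Study. That is 1 + 4 + 2 + 1 + 1 = 9. Using Day 1 pre-PM as baseline leaves 9 − 1 = 8 per subject. If only the visits listed in SAP Appendix 1 are shown (no Days 2, 4 or 6), 4 remain: Day 7 pre-AM, Day 7 pre-PM, Day 8 and End of Study. With 8 subjects per cohort and nothing missing, this is 4 × 8 = 32 to 8 × 8 = 64 values per variable per cohort. Subjects who stay in the unit throughout would have more. These are counts of affected values, not the size of an effect.

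**Other scheduled measures, with Day 1 values eligible**

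- ECG: the only Day 1 recording is predose (Table 12-1, footnote 7), so it is the protocol baseline.
- Laboratory: Table 12-1 marks Day 1 and Table 12-2 lists no Day 1 sample. Footnote 5 places samples on dosing days in the morning before the dose. Either way, no scheduled Day 1 sample follows the first dose.
- Respiratory rate and temperature: footnote 8 does not schedule them on Day 1.

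**Unscheduled values.** SAP 6.3 admits unscheduled assessments to baseline, and protocol 6.1.3 permits confirmatory repeats of vital signs. Any unscheduled or repeat value taken on Day 1 after dosing would meet the same gap.

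**Companion document.** PK/PD SAP 6.3 has similar date-based wording, but its 15.1 restores the value before first administration, apart from the time-matched rule for urine osmolality. The Non-PK/PD SAP has no corresponding sentence.

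**The case against.** The best defence is that this is loose wording, not a different analysis. The SAP is written on protocol version 5 and declares no meaningful change, so a programmer should take the last measurement to mean the last one before treatment and code the Day 1 AM predose value. SAP Appendix 1 uses hour-level labels such as Day 1 (0 hr), and the output templates, which are not in the file, may identify the timepoint. This stands as evidence of intent. It does not supply the missing condition: the same-day sentence separates measurements from adverse events and medications by date alone, and the Appendix 1 labels do not define baseline.

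A reader might infer that ECG and laboratory baselines are also wrong, falling back to Screening and Day -1. That requires reading 6.3 as barring all Day 1 values. The same-day sentence would then have almost no function, and its contrast with adverse events and medications points the other way. The documents do not support extending the point that far.

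A reader might also infer that the safety conclusions are at risk. SAP 16 plans no statistical comparisons by default, and actual values, markedly abnormal incidences, listings and adverse event tables do not use this baseline. A lingering first-dose effect on seated pressure or pulse is possible, but nothing in the documents demonstrates it.

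**Conclusion.** The point holds for scheduled systolic pressure, diastolic pressure and pulse. As written, Non-PK/PD SAP 6.3 makes a reading taken 8.75 to 10.25 h after first exposure the literal baseline, contrary to protocol 7.7.3, while 3.3 reports no meaningful change. It should be fixed, because a stated rule gives the wrong value for part of a primary endpoint.

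The consequence is modest: descriptive change-from-baseline and shift tables for three variables, plus any unscheduled or repeat Day 1 post-dose value. The shift equals minus the Day 1 difference, and its size cannot be derived from the documents. If the programmer codes the protocol baseline, as 3.3 suggests is intended, nothing changes. The verdict assumes that both Day 1 readings are taken as scheduled and that nothing in the unseen templates overrides 6.3.

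**What to change.** Replace the baseline wording in Non-PK/PD SAP 6.3 with:

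> Baseline is the last non-missing value obtained before the first administration of study drug (the Day 1 AM dose). For blood pressure and pulse this is the Day 1 pre-AM-dose reading, or the last earlier value if that is missing. The Day 1 pre-PM-dose reading, and any other Day 1 value not shown by time or by the Day 1 AM predose label to precede the first dose, are post-baseline.

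The AM label must be explicit, because both scheduled Day 1 readings precede a dose and a bare predose label would admit either. A label is also safer than relying on clock times alone. Protocol 5.3 records dose times and 6.1.8.1 records sample times, but the documents do not show that clock times of vital signs are recorded.

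The cost is a short rewording and one selection rule in the code. No new assessment is needed, provided the two Day 1 readings are labelled or timed in the database. PK/PD SAP 6.3 can be aligned for consistency only, since its 15.1 already restores the dose-based rule.
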